4.1 Inclusion Criteria

4.1.1 Age:

4.1.1.1 **Part A1:** Patients must be \geq 12 months and \leq 21 years of age at the time of study enrollment.

4.1.1.2 **Part A2:** Patients must be \geq 6 months and $<$ 12 months of age at the time of study enrollment. Patients will enroll one dose level behind the dose level at which patients in Part A1 are enrolling.

4.1.2 Diagnosis: Patients with recurrent or refractory solid tumors, including CNS tumors and lymphoma, for which no standard therapy is available are eligible. Patients must have had histologic verification of malignancy at original diagnosis or relapse except in patients with intrinsic brain stem tumors, optic pathway gliomas, or patients with pineal tumors and elevations of CSF or serum tumor markers including alpha-fetoprotein or beta-HCG.

4.1.3 Disease Status: Patients must have either measurable or evaluable disease (see [Section 12.2](#) and [Section 12.3](#) for definitions).

4.1.4 Therapeutic Options: Patient's current disease state must be one for which there is no known curative therapy or therapy proven to prolong survival with an acceptable quality of life.

4.1.5 Performance Level: Karnofsky \geq 50% for patients $>$ 16 years of age and Lansky \geq 50 for patients \leq 16 years of age (see [Appendix I](#)). **NOTE:** Neurologic deficits in patients with CNS tumors must have been relatively stable for at least 7 days prior to study enrollment. Patients who are unable to walk because of paralysis, but who are up in a wheelchair, will be considered ambulatory for the purpose of

assessing the performance score.

4.1.6 Prior Therapy

4.1.6.1 Patients must have fully recovered from the acute toxic effects of all prior anti-cancer therapy and must meet the following minimum duration from prior anti-cancer directed therapy prior to enrollment. If after the required timeframe, the numerical eligibility criteria are met, e.g., blood count criteria, the patient is considered to have recovered adequately.

- a. Cytotoxic chemotherapy or other anti-cancer agents known to be myelosuppressive. At least 21 days after the last dose of cytotoxic or myelosuppressive chemotherapy (42 days if prior nitrosourea). See DVL homepage for commercial and Phase 1 investigational agent classifications. For agents not listed, the duration of this interval must be discussed with the study chair and the study assigned Research Coordinator prior to enrollment.
- b. Anti-cancer agents not known to be myelosuppressive (e.g. not associated with reduced platelet or ANC counts): ≥ 7 days after the last dose of agent. See DVL homepage for commercial and Phase 1 investigational agent classifications. For agents not listed, the duration of this interval must be discussed with the study chair and the study assigned Research Coordinator prior to enrollment.
- c. Antibodies: ≥ 21 days must have elapsed from infusion of last dose of antibody, and toxicity related to prior antibody therapy must be recovered to Grade ≤ 1 .
- d. Corticosteroids: See [Section 4.2.2.1](#). If used to modify immune adverse events related to prior therapy, ≥ 14 days must have elapsed since last dose of corticosteroid.
- e. Hematopoietic growth factors: ≥ 14 days after the last dose of a long-acting growth factor (e.g., pegfilgrastim) or 7 days for short-acting growth factor. For agents that have known adverse events occurring beyond 7 days after administration, this period must be extended beyond the time during which adverse events are known to occur. The duration of this interval must be discussed with the study chair and the study assigned Research Coordinator.
- f. Interleukins, Interferons and Cytokines (other than Hematopoietic Growth Factors): ≥ 21 days after the completion of interleukins, interferon or cytokines (other than Hematopoietic Growth Factors).
- g. Stem cell Infusions (with or without TBI):
 - Allogeneic (non-autologous) bone marrow or stem cell transplant, or any stem cell infusion including DLI or boost infusion: ≥ 84 days after infusion and no evidence of GVHD.
 - Autologous stem cell infusion including boost infusion: ≥ 42 days.

- h. Cellular Therapy: ≥ 42 days after the completion of any type of cellular therapy (e.g., modified T cells, NK cells, dendritic cells, etc.)
- i. XRT/External Beam Irradiation including Protons: ≥ 14 days after local XRT; ≥ 150 days after TBI, craniospinal XRT or if radiation to $\geq 50\%$ of the pelvis; ≥ 42 days if other substantial BM radiation.
- j. Radiopharmaceutical therapy (e.g., radiolabeled antibody, 131I-MIBG): ≥ 42 days after systemically administered radiopharmaceutical therapy.
- k. Patients must not have received prior exposure to pevonedistat. Patients with prior exposure to irinotecan or temozolomide are eligible.

4.1.7 Organ Function Requirements

4.1.7.1 Adequate Bone Marrow Function defined as:

- a. For patients with solid tumors without known bone marrow involvement:
 - Peripheral absolute neutrophil count (ANC) $\geq 1000/\text{mm}^3$
 - Platelet count $\geq 100,000/\text{mm}^3$ (transfusion independent, defined as not receiving platelet transfusions for at least 7 days prior to enrollment).
 - Hemoglobin $\geq 8 \text{ g/dL}$
- b. Patients with known bone marrow metastatic disease will be eligible for study provided they meet the blood counts in [Section 4.1.7.1.a](#) (may receive transfusions provided they are not known to be refractory to red cell or platelet transfusions). These patients will not be evaluable for hematologic toxicity. At least 5 of every cohort of 6 patients on Part A1 must be evaluable for hematologic toxicity for the dose-escalation part of the study. If dose-limiting hematologic toxicity is observed, all subsequent patients enrolled must be evaluable for hematologic toxicity.

4.1.7.2 Adequate Renal Function defined as:

- Creatinine clearance or radioisotope GFR $\geq 70 \text{ mL/min}/1.73 \text{ m}^2$ or
- A serum creatinine based on age/gender as follows:

Age	Maximum Serum Creatinine (mg/dL)	
	Male	Female
6 months to < 1 year	0.5	0.5
1 to < 2 years	0.6	0.6
2 to < 6 years	0.8	0.8
6 to < 10 years	1	1
10 to < 13 years	1.2	1.2
13 to < 16 years	1.5	1.4
≥ 16 years	1.7	1.4

The threshold creatinine values in this Table were derived from the Schwartz formula for estimating GFR (Schwartz et al. J. Peds, 106:522, 1985) utilizing child length and stature data published by the CDC.

4.1.7.3 Adequate Liver Function defined as:

- Bilirubin (sum of conjugated + unconjugated) \leq upper limit of normal (ULN) for age
- SGPT (ALT) \leq 135 U/L. For the purpose of this study, the ULN for SGPT is 45 U/L.
- SGOT (AST) \leq 150 U/L. For the purpose of this study, the ULN for SGOT is 50 U/L.
- Serum albumin \geq 2.7 g/dL

4.1.7.4 Adequate Cardiac Function defined as:

- Shortening fraction of \geq 27% by echocardiogram, or
- Ejection fraction of \geq 50% by gated radionuclide study.
- No supraventricular arrhythmia on EKG
- Prolonged rate corrected QT (QTc) interval $<$ 500 msec

4.1.7.5 Adequate Pulmonary Function defined as:

- Pulse oximetry $>$ 94% on room air if there is clinical indication for determination (e.g. dyspnea at rest).

4.1.7.6 Adequate Neurologic Function defined as:

- Patients with seizure disorder may be enrolled if on non-enzyme inducing anticonvulsants and well controlled. See [Section 4.2.6.4](#) for further details.
- Nervous system disorders (CTCAE version 5.0) resulting from prior therapy must be \leq Grade 2, with the exception of decreased tendon reflex (DTR). Any grade of DTR is eligible.

4.1.7.7 Adequate Coagulation defined as:

- INR \leq 1.5

4.1.8 Informed Consent: All patients and/or their parents or legally authorized representatives must sign a written informed consent. Assent, when appropriate, will be obtained according to institutional guidelines.**4.2 Exclusion Criteria****4.2.1 Pregnancy or Breast-Feeding**

4.2.1.1 Pregnant or breast-feeding women will not be entered on this study because there is not yet available information regarding human fetal or teratogenic toxicities. Pregnancy tests must be obtained in girls who are post-menarchal.

4.2.1.2 Males or females of reproductive potential may not participate unless they have agreed to practice 1 highly effective and 1 additional effective (barrier) method of contraception at the same time during the entire study treatment period and through 4 months after the last dose of study drug, or agree to practice true abstinence, when this is in line with the preferred and usual lifestyle of the subject. Periodic abstinence (e.g., calendar, ovulation, symptothermal, post-ovulation methods), withdrawal, spermicides only,

and lactational amenorrhea are not acceptable methods of contraception.

4.2.2 Patients with uncontrolled high blood pressure (i.e., systolic/diastolic blood pressure $> 99^{\text{th}}$ percentile) are not eligible. See [Appendix XII](#) for more details.

4.2.3 Patients with known cardiopulmonary disease are not eligible. Cardiopulmonary disease is defined as:

- Cardiomyopathy other than chemotherapy related changes in cardiac function that meet the eligibility requirements in [Section 4.1.7.4](#).
- Clinically significant arrhythmia:
 1. History of polymorphic ventricular fibrillation or torsade de pointes,
 2. Permanent atrial fibrillation [a fib], defined as continuous a fib for ≥ 6 months,
 3. Persistent a fib, defined as sustained a fib lasting > 7 days and/or requiring cardioversion in the 4 weeks before screening,
 4. Grade 3 a fib defined as symptomatic and incompletely controlled medically, or controlled with device (e.g. pacemaker), or ablation and
 5. Patients with paroxysmal a fib or $<$ Gr 3 a fib for period of at least 6 months are permitted to enroll provided that their rate is controlled on a stable regimen.
- Implantable cardioverter defibrillator;
- Moderate to severe aortic and/or mitral stenosis or other valvulopathy (ongoing);
- Pulmonary hypertension
- Congestive heart failure Class III or IV (See [Appendix IX](#))

4.2.4 Patients with known hepatic cirrhosis or severe pre-existing hepatic impairment are not eligible.

4.2.5 Patients with uncontrolled coagulopathy or bleeding disorder are not eligible.

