4.0 PATIENT ELIGIBILITY

All clinical and laboratory studies to determine eligibility must be performed within 7 days prior to enrollment unless otherwise indicated. Laboratory values used to assess eligibility must be no older than seven (7) days at the start of therapy. Laboratory tests need **not** be repeated if therapy starts **within** seven (7) days of obtaining labs to assess eligibility. If a post-enrollment lab value is outside the limits of eligibility, or laboratory values are older than 7 days, then the following laboratory evaluations must be re-checked within 48 hours prior to initiating therapy: CBC with differential, bilirubin, ALT (SGPT), and serum creatinine. If the recheck is outside the limits of eligibility, the patient may not receive protocol therapy and will be considered off protocol therapy. Imaging studies must be obtained within 14 days prior to start of protocol therapy (repeat the tumor imaging if necessary).

Clarification in timing when counting days: As an example, please note that if the patient's last day of prior therapy is September 1st, and the protocol requires waiting at least 7 days for that type of prior therapy, then that patient cannot be enrolled until September 8th.

Important note: The eligibility criteria listed below are interpreted literally and cannot be waived (per COG policy posted 5/11/01). All clinical and laboratory data required for determining eligibility of a patient enrolled on this trial must be available in the patient's medical or research record which will serve as the source document for verification at the time of audit.

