Method of Administration: Patients with solid tumors, including CNS tumors and lymphoma, will receive pevonedistat IV over one hour. In Cycle 1, pevonedistat will be administered as a single agent on Day 1 and in combination with oral temozolomide and IV irinotecan on Days 8, 10, and 12. In Cycles 2+, pevonedistat will be administered in combination with oral temozolomide and IV irinotecan on Days 1, 3, and 5 (see [Appendix IV](#) for temozolomide dosing nomogram and [Section 9.4.4](#) for administration instructions for patients who cannot swallow temozolomide capsules whole). Irinotecan is administered

over 90 minutes one hour after temozolomide. Pevonedistat is administered over 60 minutes at the completion of irinotecan infusion. If emesis occurs within 30 minutes of taking a dose of temozolomide, then the dose may be repeated once. If emesis occurs after 30 minutes, the dose should not be repeated.

CYCLE 1:

Temozolomide: 100 mg/m²/dose (maximum dose 200 mg) PO daily x 5 on Days 8-12. See [Appendix IV](#) for BSA-based dosing nomograms using oral capsules.

Irinotecan: BSA-based dosing (below), IV over 90 minutes daily x 5 on Days 8-12 one hour after temozolomide.

IRINOTECAN IV 50 mg/m ² dose level	
BSA (m ²)	Dose (mg)
0.25-0.29	8
0.3-0.34	12
0.35-0.39	15
0.4-0.44	18
0.45-0.49	22
0.5-0.54	24
0.55-0.59	28
≥ 0.6	50 mg/m ²

Pevonedistat*: IV over 60 minutes on Day 1 alone and on Days 8, 10, and 12 immediately after irinotecan. Starting dose is 15 mg/m² (Dose Level 1). See Dose Escalation Schema in [Section 5.4](#).

For infusion-related reactions consider premedication with diphenhydramine for subsequent doses and increasing infusion duration to 2 hours. Other supportive care measures may be used at the investigator's discretion.

CYCLES 2+:

Temozolomide: 100 mg/m²/dose (maximum dose 200 mg) PO daily x 5 on Days 1-5. See [Appendix IV](#) for BSA-based dosing nomograms using oral capsules.

Irinotecan: BSA-based dosing (below), IV over 90 minutes daily x 5 on Days 1-5 one hour after temozolomide.

IRINOTECAN IV 50 mg/m ² dose level	
BSA (m ²)	Dose (mg)
0.25-0.29	8
0.3-0.34	12
0.35-0.39	15
0.4-0.44	18
0.45-0.49	22
0.5-0.54	24
0.55-0.59	28
≥ 0.6	50 mg/m ²

Pevonedistat*: IV over 60 minutes on Days 1, 3, and 5 immediately after irinotecan. Starting dose is 15 mg/m² (Dose Level 1). See Dose Escalation Schema

in [Section 5.4](#).

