For pevonédistat, a minimum of 1 full calendar day between any 2 doses should be maintained, and a maximum of 3 doses of pevonédistat within Cycles 2+ must not be exceeded. There should be a maximum of 13 days between doses within a given cycle.	

6.2.5 Pevonedistat dose modification for hypophosphatemia:

If hypophosphatemia is \geq Grade 3, study drug treatment should not be resumed until the hypophosphatemia is \leq Grade 2. Hypophosphatemia should be evaluated (including severity and etiology), monitored, and treated according to institutional guidelines.

6.3 Dose Modifications for Non-Hematological Toxicity (for patients < 12 months at the time of the DLT)

Patients less than 12 months of age who have a \geq Grade 2 non-hematological toxicity attributable to the study drug will have pevonedistat held as per [Section 6.2](#) and this will be considered a DLT with the specific exclusion of Grade 2 liver enzyme elevation, including ALT/AST/bilirubin, that returns to Grade \leq 1 or baseline prior to the time for the next treatment cycle (see [Section 6.2.4](#)). Patients should receive subsequent cycles of the drug but with dose modifications according to [Section 6.2](#).

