¹ Twice weekly during Cycle 1. If patients have Grade 4 neutropenia or thrombocytopenia, CBCs should be checked at least every other day until recovery to Grade 3 or until the criteria for dose limiting toxicity are met.

² If patients develop Grade 4 neutropenia, CBCs should be checked every 3 to 4 days until recovery to Grade 3.

³ If patients remain on study for $>$ 4 cycles and \geq Grade 3 cytopenias are not observed, then CBCs may be obtained at the start of subsequent cycles and as clinically indicated.

⁴ Women of childbearing potential require a negative pregnancy test prior to starting treatment; sexually active patients must use an acceptable method of birth control. Abstinence is an acceptable methods of birth control. All women of childbearing potential must have a pregnancy test done every cycle prior to initiation of a new cycle.

⁵ Tumor disease evaluation should be obtained on the next consecutive cycle after initial documentation of either a PR or CR. If the institutional investigator determines that the patient has progressed based on clinical or laboratory evidence, he/she may opt not to confirm this finding radiographically.

⁶ See [Section 8.3](#) for details.

⁷ Vital signs should be checked prior to each pevonedistat infusion. Vital signs will also be assessed at the end of treatment.

⁸ If a solid tumor patient is suspected to have or has a history of bone marrow involvement then a pre-study bone marrow biopsy and/or aspirate is required. This should then be repeated with each tumor disease evaluation if pre-study bone marrow was positive for metastatic disease.

*Check prior to each dose of pevonedistat, then weekly for remaining weeks of cycle. If patients have Grade 2, 3, or 4 ALT/AST/bilirubin on or after Cycle 1 Day 8, AST/ALT/bilirubin should be checked at least every other day until recovery to \leq Grade 1. See [Section 6.2.4](#) for more details.

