9.4.2 Toxicity

Incidence	Toxicities
Common (>20% of patients)	
• Constipation• Nausea• Vomiting• Diarrhea• Anorexia• Alopecia• Alanine aminotransferase increased• Aspartate aminotransferase increased• Ataxia• Anxiety• Depression• Insomnia• Nervous system disorders – other: hemiparesis or paresis, dizziness, gait disturbance, amnesia, paresthesia, somnolence, headache, seizure, fatigue
Occasional (4-20% of patients)	
• Edema limbs• Localized edema• Rash maculopapular• Dysphagia• Mucositis oral• Anemia• Platelet count decreased• White blood cell count decreased• Lymphocyte count decreased• Aplastic anemia• Blood bilirubin increased• Urinary frequency• Cough• Upper respiratory infection• Sinusitis
Rare (≤ 3% of patients)	
• Stevens-Johnson syndrome• Toxic epidermal necrolysis• Erythema multiforme• Hypercalcemia

	
• Lower gastrointestinal hemorrhage• Upper gastrointestinal hemorrhage• Cholecystitis• Alkaline phosphatase increased• Myelodysplastic syndrome• Leukemia secondary to oncology chemotherapy• Infections and infestations – other: Pneumocystis pneumonia, pulmonary fibrosis, anaphylaxis, allergic reaction, hepatic failure
Pregnancy & Lactation	
Pregnancy Category D
 
Adequate, well-controlled studies have not been conducted in humans. Women of childbearing potential should be advised against becoming pregnant while taking temozolomide and for at least 6 months following the end of therapy. Temozolomide administration to rats and rabbits at 3/8 and 3/4 the human dose resulted in the development of malformations of the external organs, soft tissues, and skeleton. These animal studies also demonstrated embryolethality (increased resorptions) at similar doses. There is no information available regarding the transmission of temozolomide during lactation; women should avoid breastfeeding while receiving temozolomide.

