Amendment 5 will add dose level 4 (35 mg/m²) to the dose escalation part of this study. This amendment will require a minimum of 2 evaluable patients and a maximum of 15 additional patients. The maximum includes 6 patients at dose level 4, 6 additional patients for PK analysis, and 20% inevaluability. The current enrollment rate is approximately 1 patient per month, and this number is expected to be accrued within 15 months. If dose level 4 is expanded to 12 patients due to DLTs of different classes, then the absolute maximum number of patients enrolled is 23. This would require up to 23 months for accrual.

Part A2 is expected to enroll a maximum of 15 patients including 6 at dose level 3, 6 at dose level 4, and 20% inevaluability.

As of 6/30/19, total of 18 patients have been enrolled in Part A1. No patients have enrolled in Part A2. Therefore, the maximum number of patients required to complete this study overall is expected to be 48, and the absolute maximum is 56.

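### The contraception entry rule stops at 4 months after the last dose, while the protocol's own temozolomide advice for women runs to at least 6 months

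*Combined protocol and SAP*

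**What the plan says.** Section 4.2.1.2 makes entry for males and females of reproductive potential conditional on agreeing to one highly effective and one barrier method during treatment and "through 4 months after the last dose of study drug". True abstinence is allowed as an alternative. The criterion does not say which agent or agents count as study drug. The note at the head of section 4.0 reads: "The eligibility criteria listed below are interpreted literally and cannot be waived".

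Temozolomide belongs to the regimen. Under section 5.1, in Cycle 1 pevonedistat "will be administered as a single agent on Day 1 and in combination with oral temozolomide" and irinotecan from Day 8. In later cycles it is again given in "combination with oral temozolomide and IV irinotecan on Days 1, 3, and 5". Temozolomide itself runs on Days 8-12 of Cycle 1 and Days 1-5 of each later cycle.

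The temozolomide toxicity table in section 9.4.2 classes the drug as Pregnancy Category D, describes malformations and embryo loss in animals, and states: "Women of childbearing potential should be advised against becoming pregnant while taking temozolomide and for at least 6 months following the end of therapy".

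Three other places bear on the point:

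- Section 8.1, footnote 4, says "sexually active patients must use an acceptable method of birth control" and asks for a pregnancy test before each cycle. It gives no period after treatment. The therapy delivery maps in Appendix XIII repeat it.
- Section 13.7.1 requires expedited reporting of pregnancies up to 6 months after the last dose of study therapy, because the agents may harm a fetus.
- Section 10.2 takes patients off study 30 days after the last dose of the investigational agent.

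**The concern.** The binding text and the drug-specific advice give different periods for the same women, and the binding text is the shorter. Because section 4.0 has the criteria applied literally, a female who agrees to exactly 4 months qualifies. Whether she also hears about 6 months then depends on the site acting on a drug monograph, or on consent wording that cannot be seen here.

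The risk is fetal exposure to an alkylating agent. Months 4 to 6 fall after the patient has left the study, with no scheduled visit or pregnancy test, so what she agreed to and was told is the main protection. The protocol already works to 6 months when it asks for pregnancies to be reported, but reporting does not prevent them.

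**Working it through.** There is no sample-size or error-rate figure to reproduce. The check sets the stated durations side by side and then asks whether any reading or dosing pattern reconciles them.

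**1. Stated durations**

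| Source | Who | Period after treatment |
|---|---|---|
| 4.2.1.2, entry criterion | males and females of reproductive potential | 4 months after study drug |
| 9.4.2, temozolomide information | women of childbearing potential | at least 6 months after temozolomide ends |
| 8.1 footnote 4 | sexually active patients | none stated |
| 9.3.2, irinotecan information | – | none stated |
| 13.7.1, pregnancy reporting | patients who become pregnant | 6 months after study therapy |

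**2. Gap under planned dosing.** The last pevonedistat and temozolomide doses fall on the same day: Day 12 in Cycle 1 and Day 5 in later cycles. Cover after temozolomide is therefore 4 months whichever agent is meant, and the gap is 6 − 4 = 2 months.

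**3. Pevonedistat given late.** Section 6.2.4 allows a dose delayed for liver tests as late as Day 25 of Cycle 1 or Day 18 of a later cycle. That is 25 − 12 = 13 days, or 18 − 5 = 13 days, after the last temozolomide dose. With a 30-day month, 13/30 = 0.4 month. Cover is then about 4 + 0.4 = 4.4 months and the gap about 6 − 4.4 = 1.6 months. This holds whether study drug means pevonedistat or all three agents.

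**4. Pevonedistat stopped early.** Section 6.3 appears to use the term for pevonedistat alone: toxicity "attributable to the study drug will have pevonedistat held". If 4.2.1.2 means the same, no period is tied to temozolomide as such. As an example, assume pevonedistat is held from Day 8 of Cycle 1 and never resumed, while temozolomide runs to Day 12. Section 6.2.4 does not say whether temozolomide continues in that case, so this is an assumption. The last pevonedistat dose (Day 1) precedes the last temozolomide dose by 12 − 1 = 11 days, or 11/30 = 0.4 month. Cover after temozolomide is about 4 − 0.4 = 3.6 months and the gap about 2.4 months. On the all-agents reading, cover stays at 4 months.

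**5. Who is outside the gap.** A patient removed before Day 8 of Cycle 1 never receives temozolomide. A patient who chooses abstinence is covered by a clause with no stated end date. Males are not named in the 6-month advice.

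**6. How many are affected.** The planned enrolment table in section 11.4 gives 22 + 0 = 22 females out of 22 + 31 + 0 + 3 = 56 patients, and 22/56 = 0.393, or 39%. This is only an upper bound, because it includes girls of all ages from 6 months. Section 11.1 adds: "Part A2 is expected to enroll a maximum of 15 patients", all infants. The documents do not give the number of reproductive potential.

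**The case against.** The strongest reply is that the two texts do different jobs. Section 4.2.1.2 sets a minimum agreement for entry, and section 9.4.2 already directs that women be advised for 6 months. Four months is a floor, so a site can satisfy both, and the literal-interpretation note governs who may enrol without limiting later counselling. All of this is true. It makes the point a mismatch and not a contradiction. It does not explain why the text that must be applied should carry the shorter period.

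The consent pages were removed and section 9.1 is redacted, so patients may well be told 6 months. That limits what can be said about actual practice. Correct consent wording would still leave the entry criterion out of step with section 9.4.2.

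Reading study drug as pevonedistat alone is uncertain. Section 11.2.1 uses a form that allows for several drugs, and section 6.3 deals with pevonedistat dosing. This stands, but the conclusion does not need that reading, because the gap under planned dosing is 2 months either way.

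The numbers are likely to be small. The 56 is the absolute maximum (18 + 23 + 15), against an expected maximum of 48 (18 + 15 + 15). Eighteen patients had already enrolled by 30 June 2019, which leaves at most 23 further non-infants of both sexes from that date. This stands, and it limits how many patients an amended criterion could reach. It does not make the shorter period right for those patients.

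Neither 4 nor 6 months is checked by scheduled visits. That is also true, and it makes the wording of the agreement matter more.

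**Conclusion.** The concern holds. For females of reproductive potential who receive temozolomide and choose contraception, the visible entry requirement falls about 2 months short of the protocol's own advice under planned dosing. The shortfall is about 1.6 months if the final pevonedistat dose is given as late as section 6.2.4 permits. It is somewhat over 2 months if study drug means pevonedistat and pevonedistat stops before temozolomide. The number affected is unknown and cannot exceed the 22 planned females.

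The conclusion assumes that neither the consent form nor the redacted pevonedistat section amends the entry requirement itself. It is a participant-safety wording defect that should be corrected. It has no effect on the MTD, the DLT rules or the PK analysis.

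**What to change.** Amend section 4.2.1.2 so that females of reproductive potential agree to contraception or true abstinence during treatment and until the later of two dates: 6 months after the last temozolomide dose, or 4 months after the last pevonedistat dose. Naming the agents removes the doubt about study drug and gives the abstinence option an end date. A female who never receives temozolomide keeps the 4-month period. Leave the male duration as it is, since section 9.4.2 gives no advice for males. Add a cross-reference to this criterion in section 8.1, footnote 4.

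The cost is one phrase and one cross-reference, plus about two more months of required contraception for the females concerned. Sample size, dose-escalation rules and analyses do not change.
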